### Approach

**Subjects** will be recruited by ads directed at parents, e.g., "Has your child developed problems from playing video games too much?" Staff will inform callers that the study involves both parent and child participation.

Inclusion criteria are: (1) parent/guardian of a 10-19 year old residing in the same household  $\geq 8$  months/year; and (2) child meets DSM-5 IGD criteria by self-report or by parent report (see below and Human Subjects).

Exclusion criteria are parent or child has a significant other mental health condition that may impact response to treatment (active suicidality, psychosis), and parent or child is unable to attend 6 sessions over 8 weeks.

Child age range spans early to late adolescence, and residential criteria ensure the child lives primarily with the target parent (allowing for visitation of divorced parents, but not boarding students). The child must meet DSM-5 IGD criteria via the self-reported or parent-reported VGDS or semi-structured interview. The self-report version of the VGDS has established psychometric properties (Rehbein et al., 2015) and we have found evidence of validity of the parent-version of the VGDS in our current pilot study, as evidence by concordance between the parent VGDS and a clinical interview administered by doctoral level clinicians.

**Informed consent.** Persons who call and appear eligible will be invited to an in-person assessment, at which we will obtain written informed consent from parents and children aged 18 years; those  $< 18$  will provide assent.

**Assessments.** Staff will administer instruments with established psychometric properties (when available) to assess study entry criteria, hypothesized mechanisms of action, and outcomes. Most measures will be collected at baseline (BL), week 4, post-treatment, and a week 24 follow-up. There are some exceptions. The demographic interview will be administered at BL only. The AUDIT, DUDIT, BRIEF, BIS-11 (parent and child versions), SRS, and the DERS will be administered at BL and post-treatment only. The SCID, TLFB, and the T-ASI will be administered at BL, post-treatment, and week 24 only. Abbreviated versions of some measures will be administered at the follow-ups. Some variability in the scheduling of the follow-ups will be allowed to account for variability between families in how quickly they complete the 6 sessions of therapy.

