Both parents may participate and will complete the parental assessments (est. 2 hours), and both (when available) can participate in the therapy, consistent with how family therapy is typically provided. Both parents and children will complete a therapy satisfaction form post treatment. Children and parents will receive \$30 in gift cards for completing the baseline assessment and the 4 week follow-up and \$50 in gift cards for the post-treatment and 24 week follow-up interviews (up to \$160/family member).

Family members may complete their follow-up measures through the survey function of REDCap in advance of their in-person meetings. When the research assistant calls to schedule the follow-ups, participants will be given the option of receiving the survey link through e-mail, receiving a paper copy of the assessments by mail, or completing the measures when they arrive for their in-person meeting. The week 4 assessment can be completed in its entirety by the participant at home through REDCap or the mail, unless the participant prefers an in-person meeting. Study visits may be completed over the phone if needed.

Parents will provide:

- basic demographics, including age, SES, gender, and education of parents and child, and indices of the child's school functioning: grades, tardiness, absences and disciplinary issues

- modified Treatment Service Review (TSR; McLellan et al., 1992) questionnaire about histories and current treatments received (of the child). Additional questions specific to treatment for video game addiction treatment will be administered at all time points.
- Parents will provide data about their own psychological symptoms (Brief Symptom Inventory [BSI]; Derogatis, 1992)
- emotional regulation (Difficulties in Emotion Regulation Scale [DERS]; Gratz & Roemer, 2004).
- Parents' perceptions of their child's gaming will be evaluated by a revised VGDS (Rehbein et al., 2015), which includes items about types and locations of all gaming devices in the home and frequencies with which they monitor their child's gaming behaviors.
- a semi-structured clinical interview using DSM-5 criteria (SCID; Petry et al., 2014), assessed over past year and past 2 months at BL and past 2 months at other time points.
- Parents will complete a TimeLine Follow-Back (TLFB; Sobell & Sobell, 1990) of the child's gaming, time spent watching others play online (e.g., YouTube, Twitch), and sleep

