- Social Phobia and Anxiety Inventory for Children (Beidel et al., 1995);
- Center for Epidemiological Studies-Depressed Mood scale (Radloff, 1977);
- Pittsburgh Sleep Quality Index (Buysse et al., 1989).
- the Youth Self-Report (Achenbach, 1991) of emotional and behavioral problems,

- DERS (Gratz & Roemer, 2004),
- quality of life KINDL-adolescent version (Ravens-Sieberer, 2000)
- the adolescent version of the Barrett Impulsiveness Scale (BIS-11), a measure of their own impulsivity (Patton, Stanford, & Barratt, 1995)

**Randomization.** After baseline, families will be randomized via a computerized algorithm (Stout et al., 1994) to groups below. Groups will be stratified by child age ( $\leq 15$  or over), sex, and parents participating (one vs. both).

**A. Referral for care.** Therapists will explain that gaming problems often co-occur with other mental health problems, and effective treatment for the latter may reduce gaming as well. Therapists will refer parents to local support groups such as Department of Mental Health and Addiction Services and National Association for Mental Illness support groups. Adolescents will be referred for appropriate services as well, e.g., depression, social anxiety, ADHD, or substance use depending on co-occurring problems.

**B. Referral plus Behavioral therapy** will consist of referral for other services plus 6 family sessions (adapted from Petry, unpublished; Appendix). In Session 1, therapists will review baseline information, refer for other services, and orient participants to treatment. They will remind parents that although they cannot prevent playing entirely, they can better understand why and when their child is playing and alter their reactions toward it, which may decrease the extent of play and problems. Therapists will describe methods to re-arrange the home to better monitor and be less conducive toward playing; this may include altering locations of or removing some (or all) gaming devices from the home. Therapists will review a tracking form and instruct parents how to and benefits of closely monitoring their child's playing. Children will be asked to keep their own log as well.

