### Data analysis

**Enhancing reproducibility.** Instruments chosen are reliable and valid, although some gaming specific instruments are new, and this study will assess their psychometric properties (see below). Careful training of evaluators will precede study initiation, and assessment interviews will be audiotaped and rated for reliability when participants agree to taping (see Human Subjects; >90% of participants agree to taping in our trials). Evaluators blind to treatment conditions will conduct assessments, and obtaining information from multiple sources (parent and child) will allow for assessment of concordance between reports (see below).

**Primary aims.** We will examine baseline (BL) indices and other services received during treatment using the Treatment Service Review, and any differences between groups that relate to outcome can be used as covariates in subsequent analyses. Analysis will be conducted on an intent-to-treat basis, using all randomly assigned subjects. We will evaluate during treatment (BL to post-treatment) and longer-term (follow-up) effects.

**Aim 1:** To evaluate the feasibility and acceptability of this intervention, the proportion assigned to the intervention who complete all 6 sessions will be examined, as will parent and child ratings of satisfaction.

**Aim 2:** To examine the effect size of the intervention on reducing game playing days and durations of play, we will analyze TLFB data collected at each assessment period, with the greater report of parent or child

used for each day. Hierarchical linear models (HLM; Gibbons et al., 1993; Raudenbush & Bryk, 2002) will compare differences between groups over time. HLM is specifically designed for repeated measures designs with missing data, allowing for intra-subject serial correlation and unequal variance and covariance structures over time by incorporating available trend data for each individual with information on the group from which the subject is drawn. Maximum likelihood estimation enables analyses to be performed for the full trial without having to drop subjects with incomplete data, and both continuous and dichotomous variables can be analyzed. The model will include factors representing group, time, and their interaction, along with any important covariates.

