##### ii. Exclusion Criteria.

Participants will be excluded if parent or child has a significant *major* other mental health condition that may impact response to treatment (including but not limited to active suicidality, psychosis, bipolar disorder), or parent or child is unable to attend 6 weekly sessions over 8 weeks.

Individuals with major acute psychiatric illnesses that may impact ability to participate in the study may not participate. Anyone with active suicidal intentions, psychosis, or bipolar symptoms, for example, will be referred for appropriate psychiatric care. If symptoms subside and patients are receiving appropriate psychiatric care, they may be reconsidered for participation in this study when stable. Parents or children with other mental disorders (substance use disorders, depression, anxiety, attention deficit hyperactivity disorder) may participate, as these other conditions are common among those with IGD. Participants will be referred for treatment of these conditions as indicated. Receipt of

other mental health treatment before and during the study period will be documented. Services Review, and any differences in mental health services that occur between groups and relate to outcomes can be controlled in analyses.

If either parent or child is unable to attend sessions regularly over the next two months, they cannot participate, or will be reassessed for eligibility after returning from extended vacations or while away.

iii. Ineligible Patients.

Some patients will choose not to enroll or will not qualify for this study. They will be referred to other facilities (e.g., other substance abuse treatment clinics or detoxification services, mental health treatment facilities) as appropriate.

iv. Treatment Clinics, Services, and Patient Population.

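### The covariate rule lets services received after randomisation into the primary Aim 2 model, and nothing says the main result is the model without them

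*Combined protocol and SAP*

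**What the plan says.** The rule stands in three places. Data analysis, Primary aims, names "other services received during treatment using the Treatment Service Review, and any differences between groups that relate to outcome can be used as covariates". Section 10 of the Detailed Data and Safety Monitoring Plan repeats it. Human Subjects 1.a.ii (Exclusion Criteria) says that "any differences in mental health services that occur between groups and relate to outcomes can be controlled in analyses".

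The same Primary aims paragraph states: "Analysis will be conducted on an intent-to-treat basis, using all randomly assigned subjects". The Aim 2 HLM follows directly: "The model will include factors representing group, time, and their interaction, along with any important covariates".

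Other relevant text:
- **Timing.** Families are randomised after baseline (Approach, Randomization), so services used during treatment are post-randomisation.
- **Referral.** Both arms include referral to other services. In describing the control arm, the plan says of co-occurring mental health problems that "effective treatment for the latter may reduce gaming as well".
- **Schedule.** "Most measures will be collected at baseline (BL), week 4, post-treatment, and a week 24 follow-up", with listed exceptions. Among these, "The SCID, TLFB, and the T-ASI will be administered at BL, post-treatment, and week 24 only". The Treatment Service Review is not among the exceptions.
- **Logistic models for IGD status.** The covariates listed are demographics and baseline indices only, so the gap concerns the HLM.
- **Exploratory label.** It covers the mechanism analyses, whose list of candidate mediators does not include services.

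**The concern.** Service use during treatment can be a consequence of allocation and, on the plan's own account, can affect gaming. It may therefore lie on the path from assignment to outcome. The rule makes services eligible when they differ by arm and relate to outcome, which are the conditions under which adjusting for them can change the group comparison. An adjusted estimate would then describe the therapy with service use held equal, not referral plus therapy against referral alone.

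Gaming days and durations are primary dependent variables. A medium or larger effect on gaming is one of the conditions for proposing a larger trial, alongside feasibility and acceptability (Specific aims). As written, the choice between adjusted and unadjusted estimates, and the way services enter, could be made after seeing the data.

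**Working it through.** The plan gives no figure for service uptake or its effect, so there is none to reproduce. Its one design figure (30 per group, d = 0.65, power .80) does not enter this argument beyond the group size. Everything below except the 30 per group and the visit schedule is an assumption, in SD units.

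**Set-up.** 30 families per arm; gaming at baseline, post-treatment and week 24, as for the TLFB; random-intercept model with group, time and group-by-time; within-family correlation 0.5. I take the group-by-time term at post-treatment as the Aim 2 effect. Let G = 1 for Group B and let S be services used during treatment.
- Services: S = −δG + noise (SD 1), so Group A uses δ SD more.
- Gaming after baseline is lowered by 0.5G + bS.
- Effect of assignment = 0.5 − bδ. With b = 0.3 and δ = 0.5: 0.5 − 0.15 = 0.35.

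**Step 1: form of entry.** Group-by-time is a within-family contrast. A term that is constant over time cancels from each family's change, so it cannot alter that contrast when data are complete. A term that is zero at baseline and S afterwards does not cancel, and the coefficient becomes the effect with S held fixed, 0.50. In 2,000 simulated trials:

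| Model | Estimated benefit |
|---|---|
| Without services | 0.35 |
| Services as time-constant main effect | 0.35 |
| Services time-varying | 0.50 |
| Services with a time interaction | 0.50 |

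The first two rows agree to rounding error with complete data. With 20% of post-baseline values missing, the mean absolute difference is about 0.01. The interaction figure falls to 0.43 if earlier services correlate 0.5 with services during treatment and also act on baseline gaming.

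**Step 2: standard error.** The variance of one family's change is 0.5 + 0.5 + 0.3² = 1.09. The standard error of the difference between arms is √(2 × 1.09/30) = 0.27.

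**Step 3: the conditional rule.** The plan states no threshold. Suppose services enter (time-varying or with a time interaction) only if they differ by arm and relate to post-treatment gaming given group and baseline gaming, each at p<0.05. This occurs in 34% of trials. In those trials the estimate averages about 0.28 without services and 0.51 to 0.53 with them. The average shift over all trials is about 0.34 × (0.52 − 0.28) = 0.08, giving 0.35 + 0.08 = 0.43.

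**Step 4: range and direction.** With time-varying entry the shift is bδ.
- For b from 0.1 to 0.3 and δ from 0.3 to 0.8, it runs from 0.1 × 0.3 = 0.03 to 0.3 × 0.8 = 0.24. Under the conditional rule the average shift runs from under 0.01 to 0.18.
- If Group B uses 0.5 SD more services, the effect of assignment is 0.5 + 0.15 = 0.65 and the adjusted figure is 0.50, so the shift reverses.
- If expected uptake is equal, the mean shift is zero.

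**The case against.** The most direct reading of the plan gives no shift. Group-by-time is the only interaction named, covariates are simply added, and services received during treatment reads most naturally as one summary per family. No section proposes time-varying entry or a services-by-time interaction. Both arms receive referral, so nothing in the documents shows that uptake will differ. The adjustment is optional, checking for imbalance in co-interventions is a reasonable aim, and this is a Stage 1 pilot of 60 families. All of that stands, and it sets the weight.

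The support for repeated service data is also thin. The sentence "Additional questions specific to treatment for video game addiction treatment will be administered at all time points" concerns added questions on gaming treatment, not the whole Treatment Service Review. What remains is that the instrument is not on the list of exceptions to the general schedule. That makes time-varying entry possible, not planned.

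A reader might infer that the plan contradicts its intent-to-treat statement. It does not: that statement fixes who is analysed and sets no limit on covariates. A reader might also infer that the Aim 2 estimate will be biased, or that the larger-trial decision will rest on a service-adjusted figure. The documents say neither; the rule only says that services can be used.

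The objection does not remove the rule. It is written in three places, it names a post-randomisation variable, and no text makes the resulting model secondary.

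**Conclusion.** The concern holds as a minor point. The plan permits adjustment of the primary Aim 2 comparison for services received after randomisation and does not say that the unadjusted or baseline-adjusted model is the main result. Harm requires two things the documents leave open: entry as a time-varying term or with a time interaction, and uptake that differs by arm. If both hold, the estimate moves away from the effect of assignment, in a direction that depends on which arm uses more services. The size cannot be derived from the documents. The illustration, 0.35 to 0.50 or to 0.43 on average under the assumed p<0.05 rule, rests wholly on assumed inputs, and both shifts (0.15 and 0.08) are below the standard error of 0.27. Confidence is moderate.

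**What to change.** Amend Data analysis (Primary aims), Human Subjects 1.a.ii and section 10 of the Data and Safety Monitoring Plan in the same way:
- Limit the covariates of the primary group comparison to a pre-specified list of pre-randomisation variables, including the stratification factors (child age group, sex, one or both parents). The services problem alone does not require the stratification factors, but a closed list has to name its members and these were used in the allocation.
- Report Treatment Service Review use by arm descriptively.
- Label any service-adjusted model exploratory, and state in advance whether services enter as time-constant, time-varying or with a time interaction.

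The cost is wording plus a few degrees of freedom with 60 families (three for the stratification factors). No new data are needed, and the service-adjusted estimate stays available as an exploratory result.

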We will also compare proportions of subjects by group who are no longer gaming problematically, i.e., child reports no current DSM-5 IGD criteria and/or <5 criteria, and parent confirms no more problems for the most conservative approach. Logistic regressions will include important demographics and baseline indices of distress and severity of problems in Step 1. Step 2 will add treatment to determine if it adds unique variance in predicting outcomes after controlling for baseline indices.

**Power analyses.** This pilot is designed to assess feasibility, acceptability, and effect sizes. Thirty subjects per group are sufficient to address the former, to estimate effect sizes, and to detect moderately large differences of Cohen's (1988)  $d = 0.65$  with Type I error rate  $\alpha = .05$ , Type II error rate  $\beta = .20$ , and power  $[1 - \beta] = .80$ . If medium or larger effect sizes are noted, a larger randomized trial will be proposed to assess long-term efficacy.

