**Exploratory aims** are to evaluate potential mechanisms of actions of the intervention including: changes in number and location of gaming devices in the home, frequency of monitoring child's game playing (via self reports in both groups, and confirmed by completed logs in Group B), child's participation in alternate activities (ACC), and parental rewarding of child behaviors and family communications (PSSS, BFAM scores). Following recommendations of Morgenstern and Longabaugh (2000) for assessing mediation, Model 1 examines whether the treatments engender differential outcomes on gaming indices (i.e., Aim 2 above). Model 2 will test if potential mediators change differentially over time by condition. For these analyses, a composite indicator for each construct will be utilized (e.g., summary scores of number/location of gaming devices, monitoring frequencies, ACC, PSS and BFAM scores). Model 3 will examine partial correlations between post-treatment scores on these indices and gaming outcomes, after controlling for baseline scores. If these three models show significant effects, the final model will assess associations between these variables and gaming outcomes. Step 1 of this model will include baseline scores of the potential mediator(s). In step 2, treatment group will be entered, and in step 3, post-treatment scores of the mediator(s) will be included, and resulting predictive power of treatment condition examined. If treatment is no longer significant and the post-treatment mediation term is significant, criteria for full mediation are met. Although we do not expect to find full mediation with this sample size, potential mediators with medium or higher effect sizes in Models 2-3 will be considered for future evaluation and inclusion in this intervention, if main effects of treatment are noted (Aim 2).

We will also assess effect sizes on secondary outcomes, e.g., substance use, psychosocial functioning and symptoms, sleep, and quality of life. HLM, outlined above, will compare groups over time on these indices.

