## 2. ADEQUACY OF PROTECTION AGAINST RISKS

### a. Recruitment and Informed Consent.

Informed Consent: A trained research staff member (Bachelors level or above), under supervision of the PI, will obtain informed consent. All potential subjects will receive an explanation of this study protocol, its potential risks and benefits, and alternative treatment available. Following resolution of any questions, parents/guardians and adult children (i.e., age 18) who agree to participate will be asked to sign the study

consent form and HIPAA document. A signed copy of the consent and HIPAA form will be given to each participant. Assent will be obtained from children under the age of 18, and both child and parent must agree to participate prior to collection of study data or randomization to a condition. As noted above, individuals who choose not to participate or who are deemed ineligible will be referred for other services as indicated.

An audiotaping section within the consent form will be utilized for recording of interactions between research staff and study patients, including baseline and follow-up interviews and therapy sessions. These audiofiles are utilized only for quality control procedures, to rate staff according to set standards in interview and treatment administration. Patients may participate in the study even if they do not choose to allow audiotaping (in our prior and ongoing studies, less than 5% of patients refuse audiotaping, and in this case both child and parent must agree or taping will not occur). The audiotaping consent section will explain that the purpose is to rate the staff member's interviewing and treatment administration skills.

b. Protection Against Risks. The following will protect against potential risks:

- i. Random group assignment is used, and about half of families will be assigned to the referral alone condition and half to the referral plus brief family behavioral therapy condition. These proportions will be outlined in the informed consent form, and patients will be made aware that they have about a 50% chance of being assigned to the family behavioral therapy condition. Patients may voluntarily end study participation if they are dissatisfied with their assignment.
- ii. The interviews and sample collections are brief, patients may skip questions or take a break if uncomfortable, and the particular instruments chosen are intended to minimize discomfort.

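### The Aim 2 hierarchical linear model estimates a separate baseline mean in each arm, so its change-from-baseline contrast is less precise than the same data allow

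*Combined protocol and SAP*

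**What the plan says.** Under Data analysis, Aim 2, the plan states that "we will analyze TLFB data collected at each assessment period, with the greater report of parent or child" taken for each day, and that hierarchical linear models "will compare differences between groups over time". The terms are then listed: "The model will include factors representing group, time, and their interaction, along with any important covariates". The same text stands in item 10 of the Detailed Data and Safety Monitoring Plan. The secondary outcomes follow the same route: "HLM, outlined above, will compare groups over time on these indices".

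The Assessments paragraph under Approach places the TLFB at baseline, post-treatment and week 24. The Randomization paragraph places allocation after baseline. Data analysis describes the effects of interest as baseline to post-treatment, and follow-up. Covariates are optional and depend on observed group differences that relate to outcome. Baseline TLFB is not named among them.

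The plan does not name the contrast that gives the effect size, does not say whether time is categorical or a trend, and does not mention confidence intervals for the effect. On size, it says: "Thirty subjects per group are sufficient to address the former, to estimate effect sizes".

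**The concern.** If baseline is one of the outcome rows and the model has a free group term, the two arms are allowed different true baseline means. The term that then isolates a post-randomisation effect is the group-by-time interaction, which subtracts the observed baseline difference in full. Because allocation follows baseline, the true baseline difference is zero by design. Estimating it adds variance and removes no bias.

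This matters because estimating the effect size is Aim 2, and a medium or larger effect leads to the proposal of a larger trial. Candidate mediators are also carried forward only if main effects of treatment are noted. With 30 families per arm, precision is scarce, and a better use of a value already collected costs nothing.

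**Working it through.** **Inputs from the documents.** 30 families per arm; standardised effect d = 0.65; α = 0.05; power 0.80 (Power analyses). Allocation about 1:1 (Human Subjects, Protection Against Risks). TLFB at three visits (Assessments).

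**Inputs assumed, because the documents do not give them.** Baseline-to-follow-up correlation r from 0.3 to 0.9; equal SDs at each visit, set to 1, unless stated; dropout as stated below.

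**The plan's own figure.** A two-sample comparison of single means with 30 per arm and d = 0.65 has power 0.80 by the t distribution if the test is one-sided. Two-sided, power is 0.70 and 38 per arm would be needed. The plan does not state sidedness, and the calculation involves neither baseline nor r. Two-sided tests are used below.

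**What the interaction estimates.** With categorical time and complete data, the contrast at a follow-up visit is (mean follow-up minus mean baseline) in one arm less the same in the other. Its variance is (2/n) × 2(1 − r). With a common baseline mean, or with baseline as a covariate, the variance is (2/n) × (1 − r²). The ratio of standard errors is √[2(1 − r)/(1 − r²)] = √[2/(1 + r)].

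With n = 30, so 2/n = 0.0667:

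| r | SE, free baseline | SE, common baseline | Ratio | Information lost, 1 − (1 + r)/2 |
|---|---|---|---|---|
| 0.3 | √(0.0667 × 1.4) = 0.306 | √(0.0667 × 0.91) = 0.246 | 1.24 | 35% |
| 0.5 | √(0.0667 × 1.0) = 0.258 | √(0.0667 × 0.75) = 0.224 | 1.155 | 25% |
| 0.7 | √(0.0667 × 0.6) = 0.200 | √(0.0667 × 0.51) = 0.184 | 1.085 | 15% |
| 0.9 | √(0.0667 × 0.2) = 0.115 | √(0.0667 × 0.19) = 0.113 | 1.026 | 5% |

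A generalised least squares calculation with three visits gives the same standard errors at r = 0.3, 0.5 and 0.7.

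**On the scale of d.** At r = 0.5, with the t multiplier of about 2.00, the 95% half-width is 0.258 × 2.00 = 0.52 against 0.224 × 2.00 = 0.45. Two-sided power at d = 0.65 is 0.70 against about 0.81. At r = 0.7 it is 0.89 against 0.93.

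**Departures from the simple case.**
- Unequal SDs: with post/baseline SD ratio k, the variances are proportional to 1 + k² − 2rk and k²(1 − r²). At k = 1.3 and r = 0.77 the regression slope on baseline, rk, is 1.00. Both are then 0.688 and there is no loss. At k = 0.7 and r = 0.5 they are 0.79 and 0.3675, a ratio of 1.47.
- Dropout: with 10% missing at post-treatment and 20% at week 24 (assumed), the ratio at r = 0.5 falls from 1.155 to 1.14 and 1.13.
- Linear time: with visits at weeks 0, 8 and 24 (assumed) and equal correlations, the interaction is a slope difference, and its standard error is 22%, 13% or 7% larger with free intercepts at r = 0.3, 0.5 or 0.7.
- A covariate main effect: it takes the same value at every visit and cancels when baseline is subtracted. In the least squares calculation it left the standard error of the contrast unchanged.

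**The case against.** The strongest reply is that the plan leaves these matters open and does not choose wrongly. It names no contrast and does not fix the coding of time, and its covariate clause could admit baseline TLFB, even as a baseline-by-visit term. This stands in part: the change-from-baseline contrast is the natural reading, not a stated commitment. But the covariate clause is optional and driven by observed differences, and a plain main effect does not recover the precision while baseline remains an outcome row.

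A reader might infer that the model throws the baseline away. It does not. A change score uses baseline with its slope fixed at 1. With equal SDs it beats a comparison that ignores baseline when r exceeds 0.5 (half-width 0.392 against 0.506 at r = 0.7, normal approximation) and does worse only below that (0.599 against 0.506 at r = 0.3).

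A reader might also infer that every interval in the trial is too wide. The logistic analysis of disorder status already controls for baseline indices, and so does mediation Model 3. Even in the hierarchical model the loss is an expectation: in simulation with 30 per arm, the change-score interval was the wider one in 99% of trials at r = 0.5 and 94% at r = 0.7.

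Finally, group-by-time models are conventional, and under randomisation the contrast is unbiased. That is correct. Chance baseline imbalance is the source of the extra variance, not a second harm.

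**Conclusion.** The point holds as one of precision. As written, the Aim 2 model and the secondary-outcome models that follow it let baseline means differ between arms, and nothing commits them to a common mean or to baseline adjustment. On the natural reading the standard error is about 24% to 3% larger than necessary for r from 0.3 to 0.9. That rests on categorical time, complete data and equal SDs. The loss is slightly smaller with dropout or a linear trend, nil at a regression slope of 1, and larger if the SD falls after baseline. The correlation and SD ratio are assumptions throughout. The documents do not support reading this as bias, as discarded baseline data, or as a plan that rules out adjustment. It should be changed, because the effect estimate decides what follows and the better model needs no new data.

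**What to change.** In Data analysis, Aim 2, and in item 10 of the Detailed Data and Safety Monitoring Plan, state that:

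- visit is a categorical factor;
- the model constrains both arms to a common baseline mean, with no group term at baseline and a group difference at each later visit;
- the group differences at post-treatment and week 24 are the TLFB effect estimates, each reported with a 95% confidence interval.

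Keeping baseline as an outcome row retains every randomised family with a baseline value, including those with no follow-up, as the intent-to-treat statement requires. A model of follow-up values only, with baseline as a covariate, would leave those families out.

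For secondary outcomes, in both places where the exploratory aims are set out, apply the same constrained-baseline model at whichever post-baseline visits the measure is collected. The visit sets differ: most measures also have week 4, while the AUDIT, DUDIT, BRIEF, BIS-11, SRS and DERS are taken at baseline and post-treatment only.

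The cost is a few sentences of analysis wording, with no added assessments, families or visits.
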